Inspired by the antibiotics-only approach results between 1956 and 2015, and with advances in radiologic imaging to diagnose and stage the progression of disease, there were six randomized trials comparing antibiotics to appendectomy among patients with AUA. These trials, all performed in Europe. 6-11 found that nearly 3 out of 4 patients in the antibiotics treatment group avoided surgery in the first year after diagnosis. A meta-analysis of five of these studies (the most recent published in 2015) found that antibiotic treatment was associated with a 46% reduction in complications and less pain and disability than routine appendectomy. 12 No participant deaths occurred in the trials, and the rates of perforation were lower among those in the antibiotic treatment group. However, existing trials suffer from important limitations. These include small sample sizes leading to indeterminate results, lack of imaging leading to potential inclusion of patients with complicated appendicitis and potentially without appendicitis at all, inexact and treatment dependent outcome definitions (rate of appendectomy) and operation/reoperation criteria, arbitrarily prolonged hospitalization, limited use of laparoscopic techniques. inadequate antibiotic regimen activity, and short-term follow-up (no studies followed patients beyond one year). Furthermore, none of these trials included keeping a record of the patient's experience with treatment in a standardized fashion. Perhaps as a result of these evidence gaps, nearly all United States (U.S.) patients with appendicitis (97.5% according to a recent California [CA]-based administrative database analysis¹³ and similar findings in Washington [WA] [personal communication [name]]) undergo appendectomy. Conversely, in Europe where the trials originated, it now appears that 1 in 5 patients with AUA are being offered the antibiotics approach.

It remains to be determined whether patient experience with the antibiotics strategy (performing appendectomy only when the patient gets worse on antibiotics or has a recurrence of disease) is "just as good as" appendectomy. This comparison should consider the overall impact of the treatment on their health, well-being, quality of life (QoL), healthcare burden, and all clinical endpoints (e.g., resolution of symptoms, need for eventual appendectomy, complications). It also remains to be determined what patient and clinical factors are associated with worse outcomes.

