5.3 Medical Record Review

Time points

Patients consenting to the study will have their EMR reviewed at (1) pre-determined time points and (2) ad-hoc time points if triggered by a survey response. RCs will conduct an EMR review to assess the following:

- Complications for patients using the National Surgical Quality Improvement Program (NSQIP) definitions and protocol as well as those complications related to antibiotic use; and
- 2. Healthcare utilization events since index hospital discharge. Details of all healthcare utilization events related to appendicitis will include the following information:
 - a. Length of stay;
 - b. Use and results of repeat imaging; and
 - c. Surgery type, if applicable.

The 3 cohorts will undergo pre-determined review at the following time points:

The e concre will andergo pre determined review at the following time points.							
	Randomized & Observational	EMR Only Cohort					
	Cohorts						
Index Visit	X	X					
Week 1	X						
Week 2	X						
Week 4	X	X					
Year 1	X						
Year 2	X	X					

As needed, ad-hoc chart review will be conducted if a patient reports an adverse event and further documentation is needed.

When possible, participants will continue to have their EMR reviewed at Year 3, Year 4, and Year 5.

Data Collection

Data is collected using the following forms:

Form	Description
Form Information	Captures information about when the form was filled out (time point), and by whom
ED Visit Form	Captures information about the hospital visit (demographics, admit/discharge times, symptoms)
Imaging Form	If patient had imaging done at any time point, captures information about the radiology tests and their findings
Laboratory Results Form	If patient had lab work done at any time point, captures information about the lab tests and their results
Index Visit Treatment Form	Filled out at the index visit only, captures information about randomization and/or cohort designation
Appendectomy Form	If patient had an appendectomy at any time point, captures information about the surgical procedure and treatment decision-making
Pathology Form	If patient had an appendectomy at any time point, captures information about the pathology results
Antibiotics Form	If patient was treated with antibiotics, captures information about the antibiotic treatment (both inpatient and at discharge)
Adverse Events Form	Captures information about adverse events at any time point

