5.4.2 Late Call Triggers (Beyond 3 Months)

Despite a requirement that all patients enrolled in the study have diagnostic imaging of the abdomen to exclude the possibility of a cancer, it is still possible that patients treated with antibiotics only may harbor an appendiceal mass. The research coordinator will alert the designated site clinician and study team if any of the following are reported any time after three months:

- 1. Complaints of signs and symptoms of recurrent appendicitis;
- 2. Unintentional weight loss of more than 15lbs; or
- 3. Diagnostic imaging consistent with appendiceal mass.

If the patient has not seen a healthcare provider to address these issues, the research coordinator will offer to connect the patient to the appropriate scheduling coordinator to make an appointment for follow-up at any of the clinical sites or the lead of the CCC.

As noted in Section 5.4.1, the research coordinator will document contacting the study team by either 1) responding to the Survey Response Review report on the CODA portal if report of the

call trigger was in response to a triggered surveyed question or 2) documenting by way of an internal study team call trigger tracking system concerns that are spontaneously reported.

Additionally, the site RC will be responsible for initiating the SAE reporting process if the reported patient concern is an SAE. See Section 9.0.

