Study Design and Treatment Allocation: This is a non-inferiority based, pragmatic, randomized controlled trial of antibiotics-first vs. appendectomy for the treatment of uncomplicated appendicitis with a concurrent observational cohort to characterize any selection bias associated with patients choosing to participate in the randomized trial, and to support the generalizability of study results. By necessity, this is an un-blinded study (patients will know if they were randomized to appendectomy or antibiotics), and analysts will know the treatment allocation of study participants. The DCC will generate and maintain randomization lists for each practice site. We will use block randomization within practice sites, with random blocks of 4, 6, or 8 subjects. Using block randomization ensures that equal numbers of subjects are randomized to the intervention and control arm and that the two groups are balanced at periodic enrollment intervals. We will also stratify randomization on presence appendicolith determined by imaging to ensure balanced across this important subgroup. Crossover, in the conventional manner, is defined treatmentassignments as a patient who is randomized to appendectomy who refuses to undergo surgery or someone who is randomized to antibiotics but chooses appendectomy before or after the antibiotics are started. Please see below for our specific definition of protocol compliance that will be used for a per-protocol analysis.

Outcome Measures: The primary outcome is the EQ-5Dat 4 weeks following randomization to treatment. Secondary patient reported outcome measures include the 10 PROMIS Global Health Short Form, the Decision Regret Scale, Gastrointestinal Quality of Life Index (GIQLI), healthcare utilization, days missed of work, days a caregiver missed of work, and work productivity. Clinical endpoints include: resolution of symptoms, rates of appendectomy, rates of appendicitis-related events (e.g., perforated appendicitis, additional course of antibiotics, more extensive surgical procedure, and drainage procedures), extent of operative and surgical complications, neoplasm and other pathology findings, adverse and serious adverse events, hospital days, clinic visits, and caregiver/patient "time in healthcare".

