Aim 2 Analysis Plan: Clinical endpoints (see Outcome Measures above) will also be compared between ITT groups using regression models appropriate to each endpoint (e.g., linear, logistic, Poisson, or Cox proportional hazards regression models), along with a similar non-inferiority framework with margins based on MCIDs when available. **For Sub Aim 2**, we will similarly evaluate clinical endpoints among the cohort with and without appendicolith. The goal is to estimate treatment effects within each subgroup based on appendicolith.

Exploratory Aim B Analysis Plan: One assumption is that patients included in the randomized trial are sufficiently similar to those from the general population of patients with appendicitis. Using simple univariate descriptive and comparative statistics (e.g., t-tests, Chi-squared tests), we will compare randomized patients to those in the parallel observational cohort to identify selection bias. We will also compare the primary outcome measures between randomized and non-randomized patients by examining the entire trajectory of EQ-5D QoL measurements using linear mixed effects models or GEE for longitudinal data, providing an assessment of differences in the rate of change of quality of life. We will adjust for patient- or provider-level characteristics found to be differentially represented in RCT. Using methods similar to those described in the plan for Aim 1 Secondary Analyses, we will adjust for treatment received to fully assess whether patients who participate in the RCT have a different outcome trajectory than patients in the observational cohort.

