Missing Data: We will conduct a missing data analysis to describe andcharacterize enrolled participants who do not provide data due to attrition. Specifically, we use 10-fold multiple imputation to assess the robustness of the results when missing data are imputed. In addition, as described by Molenberghs and Kenward (2007), we will also use inverse probability weighting in secondary analysis within each longitudinal regression model to inflate the weights of cases that are under-represented in the analysis due to selective attrition and/or non-participation. We will assess the sensitivity of inferences made from missing data first by using the two previously described methods for dealing with missing data and second, by imputing missing data under both pessimistic and optimistic scenarios to provide bounds on the statistical uncertainty. The characteristics of non-responders will be summarized in our final report and we will present the sensitivity of the estimated treatment effect due to alternative missing data methods.

Additional Exploratory Subgroups: We will also evaluate outcomes in selection subgroups including advanced age, sex, comorbid conditions and insurance status. For these analyses we will focus on evaluation of statistical interactions with treatment to assess treatment effect heterogeneity.

Statistical Analysis Plan References

1. Rabin R, de Charro F. EQ-5D: a measure of health status from the EuroQol Group. Ann Med. 2001 Jul;33(5):337-43. PMID:11491192

4. International Conference on Harmonisation E9 Expert Working Group. (1999). ICH harmonised tripartite guideline: statistical principles for clinical trials. Stat Med 18(15):1905-42. PMID:10532877

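### Neoplasm and other pathology findings are compared between randomised arms, but histology exists only after appendectomy, so equal disease will tend to look rarer on antibiotics

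*SAP*

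**What the plan says.** In the final SAP, the Outcome Measures paragraph includes "neoplasm and other pathology findings, adverse and serious adverse events" in its list of clinical endpoints. The Aim 2 Analysis Plan then covers the whole list at once: "Clinical endpoints (see Outcome Measures above) will also be compared between ITT groups using regression models appropriate to each endpoint". It adds a non-inferiority framework where an MCID-based margin is available. For Sub Aim 2 it states: "The goal is to estimate treatment effects within each subgroup based on appendicolith". No endpoint on the list is treated differently.

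Protocol section 5.3 describes the Pathology Form thus: "If patient had an appendectomy at any time point, captures information about the pathology results". Protocol section 2.0 reports from earlier trials that "nearly 3 out of 4 patients in the antibiotics treatment group avoided surgery in the first year after diagnosis".

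Protocol section 5.4.2 accepts that "it is still possible that patients treated with antibiotics only may harbor an appendiceal mass". One of its late triggers for alerting the site clinician is "Diagnostic imaging consistent with appendiceal mass". Section 5.4.3 encourages possible further imaging or colonoscopy in unoperated patients with persistent symptoms at or after one year, and section 6.2.1 lists appendiceal cancer as a monitored event.

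The SAP's Missing Data section sets out to describe "enrolled participants who do not provide data due to attrition".

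**The concern.** Whether an appendix is examined under the microscope is a consequence of the assigned strategy. Nearly everyone in the appendectomy arm is expected to have a specimen; most of the antibiotics arm is not. Randomisation balances true disease between the arms but not the chance of finding it. A regression on all randomised patients compares findings, and findings equal disease times detection.

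Neither document says how a patient without a specimen is coded. Coding such patients as negative under-counts disease on antibiotics. Restricting to operated patients does not repair this, because operated antibiotics patients are a selected group. The per-protocol analysis is of EQ-5D and the as-treated analysis is of the primary outcome, so neither addresses it.

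At stake is the reading of a cancer-related secondary outcome. The bias runs towards the strategy under test, and disease that was missed could be reported as disease that did not occur.

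**Working it through.** The documents give no neoplasm or pathology rate and no power statement for this endpoint, so there is no stated figure to reproduce. What follows is an illustration with equal true disease in both arms.

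**Inputs**
- Patients per arm: 1552 / 2 = 776 (protocol 8.5, with the equal allocation of 8.1).
- Share of the antibiotics arm with a specimen, *s*: 25%, from the three-in-four figure in protocol 2.0. A value of 60% is an assumption for longer follow-up with appendicolith patients included.
- Share of disease in unoperated patients found by other routes, *d*: 0, 25%, 50% (assumed).
- True rate *p*: 0.5%, 1%, 2% (assumed). Tumour visible on imaging is excluded at baseline (protocol 4.3), so low rates deserve the most weight.
- Appendectomy arm fully examined (assumed).

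**Step 1. Expected detected risk ratio, antibiotics over appendectomy; the true ratio is 1**

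Detected rate on antibiotics = *p* × [*s* + (1 − *s*) × *d*], so the expected ratio is the bracket.
- *s* = 25%, *d* = 0: 0.25
- *s* = 25%, *d* = 25%: 0.25 + 0.75 × 0.25 = 0.4375
- *s* = 25%, *d* = 50%: 0.25 + 0.75 × 0.50 = 0.625
- *s* = 60%, *d* = 0: 0.60
- Disease twice as common in the operated quarter as in the whole arm, *d* = 0: 0.25 × 2 = 0.50

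**Step 2. Expected detected cases in the first scenario (appendectomy v antibiotics)**
- *p* = 0.5%: 776 × 0.005 = 3.9 v 3.88 × 0.25 = 1.0
- *p* = 1%: 7.8 v 1.9
- *p* = 2%: 15.5 v 3.9

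**Step 3. Chance of a falsely significant lower result on antibiotics**

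This is the exact sum of binomial probabilities over all pairs of counts with fewer cases on antibiotics and two-sided Fisher p < 0.05.

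| Scenario | Expected ratio | *p* = 0.5% | *p* = 1% | *p* = 2% |
|---|---|---|---|---|
| 25% examined, no other detection | 0.25 | 0.092 | 0.346 | 0.718 |
| 25% examined, other routes find a quarter | 0.44 | 0.051 | 0.166 | 0.378 |
| 25% examined, other routes find half | 0.63 | 0.029 | 0.075 | 0.155 |
| 60% examined, no other detection | 0.60 | 0.031 | 0.083 | 0.177 |
| Disease twice as common in the operated quarter | 0.50 | 0.042 | 0.128 | 0.287 |
| Equal detection (reference) | 1.00 | 0.009 | 0.013 | 0.016 |

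**Step 4. Sensitivity to the test**

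An unpooled Wald interval for the risk difference gives 0.25, 0.46 and 0.79 in the first row. It should not be used at these counts. At *p* = 0.5%, 0.206 of its 0.245 comes from tables with no antibiotics-arm case, where that arm contributes no variance. For example, 4 v 0 puts the upper Wald limit just below zero, yet Fisher gives p = 0.12.

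**Step 5. Why a per-appendectomy rate does not settle it**

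With a true rate of 1% in both arms and disease twice as common in the operated quarter, the rate per appendectomy is 2 × 1% = 2.0% on antibiotics against 1.0% in the appendectomy arm. The distortion then runs the other way.

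**The case against.** The strongest counter-argument is that this is a pragmatic comparison of two initial strategies, and findings detected per randomised patient are a legitimate outcome of a strategy. That stands. A reader might infer that the endpoint must come out of the intention-to-treat regression; the documents do not support going that far. The defect lies in the undefined status of unexamined patients and in the absence of any label saying that the contrast concerns detection.

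A reader might also infer that a false significant result is likely. That needs a residual rate of 1% to 2%, few operations and little other detection. No rate is documented, visible tumour is excluded at entry, and sections 5.4.2, 5.4.3 and 6.2.1 give other ways for a neoplasm to surface. These routes are incidental or symptom-driven, so they narrow the gap without closing it.

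Nor do the documents support the inference that antibiotics would be declared non-inferior for cancer: margins apply only when available, and none is given for this endpoint. The treatment-effects sentence is general wording for Sub Aim 2. The protocol's own warning about a remaining mass also makes a reading of benefit less likely, though the planned analysis carries no such warning.

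Finally, the Missing Data section is not confined to drop-out. It also names non-participation and plans optimistic and pessimistic imputation, which could be extended to absent specimens. The SAP does not say it will be, and a fully followed unoperated patient fits neither description.

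**Conclusion.** The concern holds as one of differential detection. With equal true disease, the planned between-arm estimate for neoplasm and other pathology findings is biased towards fewer findings on antibiotics, with expected detected ratios of 0.25 to 0.63 over the scenarios examined. The direction follows from the documents; the size depends on assumed disease rates, on the share operated on and on how much is found without surgery. At a true rate of 0.5% the chance of a falsely significant result is 0.03 to 0.09 against about 0.01 with equal detection, so the harm there is a misleading estimate more than a false claim. At 2% the chance is 0.16 to 0.72.

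The point does not reach the primary EQ-5D analysis. It does not extend to perforation, which has other routes of capture, or to endpoints such as surgical complications that an unoperated patient truly does not have. The change should be made, with medium confidence in its practical size.

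**What to change.** In the Aim 2 plan, overall and by appendicolith status:
- State that neoplasm and other pathology findings will not be interpreted as a treatment effect on disease.
- Report them by arm as *detected* findings, per randomised patient and per appendectomy performed. Show the number of patients with a specimen and the source of detection (pathology, imaging, other work-up).
- Define a patient with no specimen and no other detection as *not detected*.
- If a between-arm estimate per randomised patient is kept, use an exact or small-sample method, call it a difference in detection under the two strategies, and draw no benefit or non-inferiority conclusion from it.
- Beside the per-appendectomy rates, state that operated antibiotics patients are a selected group.

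The cost is SAP wording and table layout. The price is that this secondary endpoint then has no between-arm test of disease.

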An additional rationale for this study is to address limitations of prior trials. To avoid misclassification problems of other trials and consistent with U.S. norms,, all patients will undergo standard radiographic imaging including CT, ultrasound (US), or magnetic resonance imaging (MRI). Patients with an appendicolith will be included in the trial but considered a unique subgroup and will be evaluated as part of a pre-specified analysis (potentially excluding them from future recruitment if an early analysis demonstrates futility related to the primary antibiotic approach not being successful). To reflect usual and emerging techniques in treatment, the study includes both types of appendectomy (open and laparoscopic) and a broad range of antibiotic strategies including the option for an "all outpatient" treatment schedule with once daily dosing of longer-acting agents. Patients in the antibiotics arm will be given a minimum of 24 hours of intravenous (IV) antibiotics (using any appropriate dosing schedule and based on the patient's ability to tolerate oral medication), followed by oral antibiotics for a total of 10 days of antibiotic treatment). Discharge from the hospital or emergency department (ED) or a change in treatment arm will be guided by clinical targets and reasons for change in treatment arms will be assessed. Participants will be followed for up to two years to assess for longer-term complications, eventual appendectomy (performed anywhere), QoL, gastrointestinal symptoms, and decisional regret. To quantify selection bias and to promote generalizability, all patients approached for the study and those who refuse randomization will be characterized at baseline. A parallel cohort of patients who refuse randomization (up to 250 who initiate the antibiotics strategy and 250 who select to undergo the appendectomy strategy) will be surveyed for up to two years. Participants in all cohorts will be given the option to participate in an extended followup that will assess long term complications, eventual appendectomy, QoL, and gastrointestinal symptoms.

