4.4.2 Those who Decline Randomization

Depending on the site, participants who decline randomization will be approached to provide consent to the observational cohort. As many as 500 will be consented into an observational

cohort study. Recruitment will be capped by treatment choice, site location, and time. Once the cap has been reached, participants will be offered participation in the EMR review only cohort.

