- 5. Exploratory Aim B One assumption is that patients included in the RCT are sufficiently similar to those from the general population of patients with appendicitis. Using simple univariate descriptive and comparative statistics (e.g., t-tests, Chi-squared tests), we will compare randomized patients to those in the parallel observational cohort to identify selection bias. We will also compare the primary outcome measures between randomized and non-randomized patients by examining the entire trajectory of EQ-5D QoL measurements using linear mixed effects models for longitudinal data, providing an assessment of differences in the rate of change of QoL. We will adjust for patient- or provider-level characteristics found to be differentially represented in RCT. Using methods similar to those described in the plan for Aim 1 Secondary Analyses, we will adjust for treatment received to fully assess whether patients who participate in the RCT have a different outcome trajectory than patients in the observational cohort.

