8.5 Sample Size and Statistical Power

Prior studies suggest that non-clinical outcomes (e.g., loss of time from work and pain scores) were similar between groups, but did not evaluate a global QoL measure. The EQ-5D QoL

index ranges from 0 (worst QoL) to 1 (highest QoL), where anchor-based methods have shown that the MCID ranges 5%-10%. Based on data from a prior study of appendectomy with EQ-5D scores at 12 weeks, we estimate that the mean EQ-5D for appendectomy patients will be 0.90 with a standard deviation of 0.12. In order to assess QoL differences between interventions, we will recruit a total of 1552 patients assuming a 90% follow-up at four-weeks. This gives the study high power (>99%) to rule out EQ-5D differences between-groups as small as 5% (e.g., if we observe treatment differences of 0 to 2%) and 80% power if we observe a treatment difference of 3% (Table 5, below).

Previous Washington State evaluations of patients undergoing appendectomy (Table 1). identified that 2-3% of the population is African American, 10-12% Hispanic, 10-15% are Medicaid beneficiaries, and 10% will be above 64 years of age. Recruiting 1552 total patients will allow for a subgroup evaluation based on older age and Medicaid beneficiary status. Assuming 50% recruitment of these populations we anticipate including ~500 Medicaid beneficiaries and ~450 patients ≥65 years. As demonstrated in Table 5, this study also has adequate power (>80%) to rule out differences of 5% for observed treatment effect of Δ =0% within subgroups as small as n=250 patients, or treatment differences of Δ =-1% within subgroups of at least n=400. For this reason, we expect the study will be able to assess these two subgroups. All other subgroup evaluations will be post hoc and used for hypothesis development only.

Table 5. Statistical Power to Declare Non-inferiority on Patient-reported QoL, Overall and by

Subgroup (Non-inferiority Margin, M = -5%, one-sided α =0.025).

Treatment Difference A	Overall		Subgroups	
Treatment Difference, Δ	N=1552	N=250	N=400	N=500
-3%	82.6%	-	-	-
-2%	99.4%	-	57.1%	67.9%
-1%	100%	62.4%	83.8%	91.4%
0%	100%	83.0%	96.4%	98.8%

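### Exploratory Aim B judges selection bias by unadjusted tests against an observational cohort limited by site, time and treatment choice, so differences between sites may be mistaken for patient self-selection or may hide it

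*SAP*

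**What the plan says.** The final SAP (Exploratory Aim B Analysis Plan) and Protocol section 8.3, item 5, describe the same first step. The method is "Using simple univariate descriptive and comparative statistics (e.g., t-tests, Chi-squared tests", and the purpose is given as: "we will compare randomized patients to those in the parallel observational cohort to identify selection bias". Neither text stratifies by site or enrolment period, and neither limits the randomised side to places or times in which the observational cohort was recruiting.

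Protocol section 4.4.2 governs who can be in that cohort:

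- The offer varies between sites: "Depending on the site, participants who decline randomization will be approached to provide consent to the observational cohort".
- The total is limited to 500 patients, with further limits inside it: "Recruitment will be capped by treatment choice, site location, and time".
- A decliner who arrives after a limit is met takes another route: "Once the cap has been reached, participants will be offered participation in the EMR review only cohort". Such a patient is therefore outside the Aim B comparison.

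Protocol section 2.1 gives the ceilings by treatment chosen: "up to 250 who initiate the antibiotics strategy and 250 who select to undergo the appendectomy strategy".

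Aim B has a second step, a comparison of EQ-5D trajectories between randomised and observational patients. That step is adjusted for treatment received and for patient or provider characteristics that were found to differ. Site and period are not named.

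**The concern.** Both documents give the observational cohort two purposes: to characterise the selection that comes from patients' choice to join the trial, and to support generalisability. A raw difference between the groups answers that question only if they were drawn from the same sites over the same time. Otherwise it combines who declines randomisation with where and when the cohort was open, and only the first of these is self-selection.

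The second step does not clear this up. Its covariates are those that the first step flags, so a confounded screen decides what is adjusted for. The same error can also run the other way: a shift in site mix can cancel a real difference within sites.

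What is at stake is the trial's statement on selection and generalisability, not its primary result.

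**Working it through.** **1. The plan's own figures.** Summing the 12 site rows of Protocol Table 1 gives 2200 cases a year, 761 Hispanic (34.6%), 558 Medicaid (25.4%) and 278 older than 65 (12.6%). These match the All Sites row.

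**2. Split by region (Table 1).**

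| | n per year | Hispanic | Medicaid |
|---|---|---|---|
| Washington, 9 sites | 1356 | 113 (8.3%) | 136 (10.0%) |
| California, 3 sites | 844 | 648 (76.8%) | 422 (50.0%) |

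The California share of volume is 844/2200 = 38.4%. Single sites range from 1.1% to 87.1% Hispanic and from 0% to 78.3% Medicaid.

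**3. What the planned test returns when there is no self-selection within region.** From the documents: 1552 randomised ("we will recruit a total of 1552 patients assuming a 90% follow-up at four-weeks") and at most 500 observational patients. Assumed: randomised patients arrive in proportion to Table 1 volume, the cohort fills to 500, and California supplies a share *s* of it. The documents give no value of *s*, so a range is shown.

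Expected observational share: p_o = p_WA + s(p_CA − p_WA). The randomised share p_r uses s = 0.384. Pearson chi-squared on expected counts, without continuity correction: χ² = (p_r − p_o)² / [p(1−p)(1/1552 + 1/500)], where p is the pooled share.

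Worked case, Hispanic, s = 0.25: p_o = 0.0833 + 0.25 × (0.7678 − 0.0833) = 0.2544 and p_r = 0.3459. The pooled share is p = 0.3236 and the standard error is √[0.3236 × 0.6764 × (1/1552 + 1/500)] = 0.0241. So z = 0.0915/0.0241 = 3.80, χ² = 14.45 and p = 0.0001.

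| s | Hispanic, randomised vs observational | p | Medicaid, randomised vs observational | p |
|---|---|---|---|---|
| 25% | 34.6% vs 25.4% | 0.0001 | 25.4% vs 20.0% | 0.015 |
| 30% | 34.6% vs 28.9% | 0.018 | 25.4% vs 22.0% | 0.13 |
| 35% | 34.6% vs 32.3% | 0.34 | 25.4% vs 24.0% | 0.55 |
| 60% | 34.6% vs 49.4% | <0.00001 | 25.4% vs 34.0% | 0.0002 |

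Masking follows from the same figures. At s = 30%, site mix alone lowers the observational Hispanic share by 34.6 − 28.9 = 5.7 points, so a true excess of 5.7 points among decliners within sites would be cancelled.

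**4. All 12 sites separately.** This used 2000 simulated trials per scenario, the same group sizes, no self-selection within any site, and a two-sided 5% level. That level is an assumption, because the documents set none for Aim B. The table shows how often the unadjusted test declares a difference.

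| Observational site mix (assumed) | Hispanic | Medicaid | Over 65 |
|---|---|---|---|
| Same as randomised | 5% | 5% | 5% |
| Equal numbers per site | 91% | 38% | 15% |
| One site (Harbor-UCLA) not contributing | 86% | 20% | 16% |
| California sites at half weight | 99% | 78% | 25% |
| Washington sites only | 100% | 100% | 88% |

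A Cochran-Mantel-Haenszel test stratified by site gave 3.9% to 5.1% across all the scenarios run.

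The documents give nothing from which the effect of enrolment period could be sized.

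**The case against.** Several objections have force.

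- **The mixes may not differ.** Section 4.4.2 does not say how the site and time caps are set. Caps in proportion to volume would keep the mixes close, and the cohort is described as concurrent. The shares used above are hypothetical, and Table 1 lists potential sites only. This stands as a limit on size. The plan still has no safeguard if the mixes differ, and site-dependent enrolment makes a difference likely.
- **Hispanic ethnicity and Medicaid are the sharpest cases.** They differ strongly between regions. For age over 65, the three intermediate scenarios give only 15% to 25%. This also stands.
- **Aim B already adjusts.** This is true of the EQ-5D trajectory, including for treatment received, so it would be wrong to call the whole of Aim B unadjusted. But the step that identifies selection bias has no adjustment. Provider-level characteristics might be taken to include site, but the text does not say so, whereas the SAP's primary model names practice site.
- **Other selection data exist.** Protocol section 2.1 promises a baseline description of everyone approached and of those who refuse, and section 4.1 requires a Screening Form for every adult with presumptive appendicitis. The SAP does not bring these data into Aim B.
- **A crude comparison is legitimate description.** It is, and it also captures differences between sites in willingness to be randomised, which a site-conditional comparison removes. Both can be reported.

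A reader might also infer that the ceilings by treatment chosen force a 50:50 mix in the cohort. The wording sets maxima: the mix is 250 to 250 only if both ceilings fill, and otherwise it still partly reflects choice.

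**Conclusion.** The concern holds as a conditional one. As written, the tests that are to identify selection bias cannot separate self-selection from differences in where and when the observational cohort was open. If the site mixes differ materially, the error can be large: with California at 25% rather than 38.4%, a 9-point Hispanic difference (p=0.0001) appears with no self-selection within region. If the mixes are close, it is small: at 35% the p-value is 0.34. The figures rest on Table 1 volumes and case mix, on randomisation in proportion to volume, on a full cohort of 500, and on assumed California shares.

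A reader might go further and conclude that the two groups do come from different sites and periods, or that some sites certainly never open the cohort. The documents make enrolment site-dependent and capped, but they record no actual mix and name no site without the cohort. Nor does the point reach the main result: Aim B is exploratory, and the primary non-inferiority analysis compares randomised arms with adjustment for site and appendicolith. The change is worth making, but it is not critical to the trial's main conclusion.

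**What to change.** In the SAP's Exploratory Aim B Analysis Plan:

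1. Keep the crude comparison, labelled as description.
2. Base any statement about selection bias on comparisons stratified by or adjusted for site. Restrict the randomised side to patients enrolled at sites, and in calendar periods, in which the observational cohort was open.
3. Put site in the EQ-5D trajectory model whatever the screening tests show.
4. Show baseline characteristics of the observational cohort by treatment chosen, because the ceilings can distort that mix.
5. As a check, repeat the comparison with EMR-only decliners added. This can use only chart-abstracted index-visit fields or Screening Form fields, since EMR-only patients complete no Baseline Assessment (Protocol section 4.4).

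The cost is SAP wording and modest extra analysis of data that the protocol already collects; item 2 also needs the dates on which the cohort was open at each site. Fewer randomised patients enter the restricted comparison, so it is less precise. It also leaves out differences between sites in willingness to be randomised, which is a reason to report the crude comparison beside it.
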